8.4 Discontinuation/withdrawal of participants and stopping rules

In consenting to the study, participants are consenting to study interventions, study follow up and data collection. However, an individual participant may stop study participation early or be stopped early for any one of the following reasons:

Any change in participant's situation that in the investigator's opinion justifies the discontinuation of study participation.

As participation in the study is entirely voluntary, the participant may choose to discontinue participation at any time without penalties or loss of benefits to which they may be entitled. Although not obliged to give a reason for discontinuing their participation a reasonable effort should be made to establish this reason, whilst remaining fully respectful of the participant's rights.

If a participant chooses to withdraw from the study, we will ask if they would be willing to complete the study feedback questionnaire at the time of withdrawal. If no follow up is possible data that has already been collected should be kept and analysed according to the ITT principle for all participants who stop follow up early.

As this is a feasibility study, once a participant has been recruited into the study and completed the first study visit (Visit 1), if a participant chooses to withdraw after this point due to non-compliance to part of the study procedures (not all), for instance non-compliance to vaginal secretion sampling or venous blood taking, we will ask if the participant is willing to continue participating in the study and complete the rest of the study procedures that the participant is willing to comply with.

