10.6.5. Sample collection and sample storage due to disruption caused by COVID-19 Pandemic

During the COVID-19 outbreak, face-to-face study visits, new recruitment and screening are suspended. Remaining participants will be offered the opportunity to continue with their study participation through the storing of their samples according to their usual study visit time-points at home until it is safe for the study team to collect the samples from the participants. This will involve the participants continuing to perform self-sampling of saliva, urine and vaginal secretions but instead of providing the samples to the research team on the day of the sampling, they will place the samples inside a securely sealed bag and store the sealed bag in the freezer at home. Participants will be provided with written instructions on how to do this and any additional sampling consumables via post. During this period of time it will not be possible to take blood samples or saliva swabs of newborns and so these will be seen as missing data points. For participants who do not agree to the storage of their samples in the freezer, or who lack access to a freezer, they will be withdrawn from the study or resume their study visits normally when it is safe to do so if suitable. Collection of home frozen samples will take place once the situation

has improved and we are able to see participants face-to-face. Participants will be contacted to update them on the changes required to the study due to the COVID-19 outbreak.

10 Safety Events

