14.2.2 Secondary endpoints

- The percentage of subjects with detectable CMV virus in saliva (measured via quantitative PCR) at individual study visits and cumulatively
- The percentage of subjects with detectable CMV virus in urine (measured via quantitative PCR) at individual study visits and cumulatively

- The percentage of subjects with detectable CMV virus in the vaginal secretions (measured via quantitative PCR) at individual study visits and cumulatively
- The quantity of CMV virus in saliva (measured via quantitative PCR) in the subjects at individual study visits cumulatively
- The quantity of CMV virus in urine (measured via quantitative PCR) in the subjects at individual study visits and cumulatively
- The quantity of CMV virus in vaginal secretions (measured via quantitative PCR) in the subjects at individual study visits and cumulatively
- Risk factors associated with CMV shedding in the subjects
- Assessment of the acceptability of the study procedures to participating pregnant women
- Proportion of subjects approached who are willing to participate in the study
- Proportion of subjects completing the study

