13.4.3 Secondary endpoint analysis

For each sample type (saliva, urine, vaginal secretions), the percentage of participating women with detectable CMV DNA as measured by quantitative PCR, will be calculated for each study visit (Visit 1, Visit 2, Visit 3, Visit 4), and cumulatively, with 95% CIs.

For each study visit (Visit 1, Visit 2, Visit 3, Visit 4), the percentage of participating women with detectable CMV DNA as measured by PCR, will be calculated for each sample type (saliva, urine, vaginal secretions), and cumulatively, with 95% CIs

CMV shedding will also be assessed quantitatively, as measured by quantitative PCR on the amount of CMV DNA detected, in each sample type and at each study visit, separately and cumulatively, with 95% CIs.

The distributions of sample type, study visit number, detectable shedding and quantity of shedding will be summarised graphically and described using means and medians, as appropriate.

Factors associated with CMV shedding as a binary outcome (detectable shedding versus no detectable shedding) will be investigated using multivariable mixed effects models. Potential risk factors will be those assessed using the study sociodemographic questionnaire at Visit 1 and risk factor questionnaires at all visits (these variables may be time-varying) – these will include ethnicity, age, number of children, parental occupation, age of child(ren), and type of handling with child(ren)'s urine and saliva.

Acceptability of the study design and procedures will be analysed descriptively, for example by calculating mean scores derived from satisfaction scales. We will also investigate factors associated with satisfaction, defined as a binary variable, using logistic regression. We will summarise free text comments made through the feedback questionnaire.

The percentage of eligible women who consent to participate, and the percentage of participants who complete the study (provide urine, saliva and vaginal secretion samples and questionnaire data at all four study visits, with or without blood and newborn saliva samples), will be calculated.

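### The completion percentage counts women withdrawn or timed out under the COVID-19 rule as ordinary non-completers, so it is biased low as a planning figure

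*Combined protocol and SAP*

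**What the plan says.** Completion is a listed secondary endpoint (14.2.2): "Proportion of subjects completing the study". Section 13.4.3 defines it as "the percentage of participants who complete the study (provide urine, saliva and vaginal secretion samples and questionnaire data at all four study visits", and the sentence continues "with or without blood and newborn saliva samples), will be calculated". The denominator is participants, with no exclusions.

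Section 10.6.5 came in with version 3.0. It states: "During the COVID-19 outbreak, face-to-face study visits, new recruitment and screening are suspended". Women already enrolled may carry on by sampling themselves and freezing the samples at home. Those who decline this, or have no freezer at home, are treated differently: "they will be withdrawn from the study or resume their study visits normally when it is safe to do so if suitable". The section's only missing-data statement concerns other items: "it will not be possible to take blood samples or saliva swabs of newborns and so these will be seen as missing data points".

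Section 8.4 says of women who stop early that "data that has already been collected should be kept and analysed according to the ITT principle for all participants who stop follow up early". Section 13.4.5 plans one further analysis, restricted to women sampled at all three time points, and does not mention COVID-19. Appendix 1 describes version 3.0 only as the addition of 10.6.5.

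**The concern.** The study exists to show whether larger multi-centre studies are feasible (5.1, 5.2, 13.2), and the completion percentage is the natural source for their attrition allowance. A woman whom the study withdraws because she has no freezer says nothing about whether women would finish four visits in ordinary times. Yet in 13.4.3 she looks the same as a woman who found the procedures too much and left. The same holds for a woman who was paused and whose visit window closed before visits resumed. A reader planning the next study would see one percentage, with no means of telling how much of the loss came from the suspension.

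**Working it through.** **Step 1: read the sections together.** No single sentence states the result; it follows from three.

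- 13.4.3: a completer needs all three maternal samples and questionnaire data at all four visits.
- 10.6.5: a woman who declines or cannot do home freezing is withdrawn, or resumes later if suitable. Its missing-data statement covers blood and newborn swabs, not maternal samples lost in this way.
- 8.4: data from women who stop early are kept. Nothing there or elsewhere removes such women from the completion denominator or reports them separately.

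A woman withdrawn under 10.6.5 before Visit 4 is therefore in the denominator and not in the numerator.

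**Step 2: which paused women are affected.** Section 9.3 gives Visit 2 a window from 17+0 to 26+6 weeks, Visit 3 a window from 27+0 weeks with no stated upper limit, and Visit 4 a window from birth to one week. A pause that outlasts the Visit 2 or Visit 4 window makes completion impossible. A shorter pause, or one that falls within the long Visit 3 window, need not.

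**Step 3: the plan's own figures.** The documents state no target or expected completion percentage, so there is none to reproduce. The one precision figure (13.3.1) is for the primary endpoint, at 30% prevalence and N = 200: 1.96 × √(0.30 × 0.70 / 200) = 6.35 points, which agrees with the stated 6 after rounding. It serves here only to confirm N = 200.

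**Step 4: formula.** Let N be the number enrolled, k the number lost under 10.6.5 (withdrawn, or paused past a window), and c the completion rate among the others. Assume the k women would also have completed at rate c had visits not been suspended.

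- Completion as defined = c × (N − k) / N
- Shortfall = c − c × (N − k) / N = (k/N) × c

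**Step 5: results.** N = 200 is the plan's target. The values of c and k are assumptions, because the documents give neither.

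| c (assumed) | k = 10 | k = 20 | k = 40 |
|---|---|---|---|
| 70% | 66.5% (−3.5) | 63% (−7) | 56% (−14) |
| 80% | 76% (−4) | 72% (−8) | 64% (−16) |
| 90% | 85.5% (−4.5) | 81% (−9) | 72% (−18) |

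For scale, the 95% half-width at c = 80% and N = 200 is 1.96 × √(0.80 × 0.20 / 200) = 5.5 points. At that rate 20 such women move the figure by 8 points, more than its sampling error; 10 move it by 4, which is less.

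Because 10.6.5 also suspends recruitment, N may end below 200, and each loss would then weigh more. With N = 150 and k = 20, 0.80 × 130/150 = 69%.

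**The case against.** The strongest reply is that this is one descriptive secondary percentage with no target, test or progression threshold, and that the numbers above are assumed. Both statements are true. If 200 women were recruited evenly over 52 weeks and followed for about 26 weeks (assumed), some 200/52 × 26 = 100 would be in follow-up at once, so k = 40 would need 40% of them to be lost under the rule. Nothing in the documents supports that, and with recruitment suspended even the 100 is not established. The table shows sensitivity, not an estimate.

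Three stronger readings are tempting, and the documents do not support them.

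- *A reader might infer that home-freezing women count as completers without the blood draw or face-to-face visit, so that the percentage pools two different procedures.* Blood and newborn saliva are outside the completion definition, and 9.2 makes blood optional from the start. Sections 9.3.2 and 9.3.3 say face-to-face contact may be unnecessary at Visits 2 and 3, and 9.3.4 ties it at Visit 4 to the newborn swab. Self-sampling is unsupervised throughout. For the items that define completion, the main changes are home freezing and later collection. No section says what a future study would require.
- *A reader might infer that every pause costs a visit.* Step 2 shows that it depends on the length and timing of the pause, and 10.6.5 expressly allows women to resume.
- *A reader might infer that every 10.6.5 withdrawal is unrelated to willingness.* Lacking a freezer is. Declining to keep samples in one's own freezer is partly a view on acceptability, which this study sets out to measure.

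The case for splitting the feedback-questionnaire scores by period does not stand either; no defect in those scores has been shown.

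What survives the reply is the reporting gap: nothing in the plan separates these women from those who chose to stop.

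**Conclusion.** The point holds in this form. Followed as written, 13.4.3 counts women withdrawn under 10.6.5, and paused women whose Visit 2 or Visit 4 window closes, together with women who chose to stop. As a planning figure for ordinary conditions the percentage is biased low by (k/N) × c.

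The direction rests on one assumption: that at least some of these women would have finished without the suspension. The size is unknown. At an assumed 80% it is 4 to 16 points for 10 to 40 women of 200, and over assumed rates of 70% to 90% it is 3.5 to 18 points. If few women were affected, it is negligible. The primary endpoint is outside this point, and the 10.6.5 rule itself is not in question, only how its consequences are reported.

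**What to change.** Keep the percentage as defined in 13.4.3, and add to that section completion, with 95% confidence intervals, in two groups:

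- (a) women whose expected delivery date plus one week fell before face-to-face visits were suspended. This is the figure for planning. Set the cut-off by expected rather than actual date: an actual-date rule would favour preterm births near the cut-off, and under 9.3.4 a preterm delivery can end follow-up before a fourth visit.
- (b) women with any visit due during the suspension.

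In (b), show 10.6.5 withdrawals and windows missed through a pause as their own category, apart from other non-completion. Within it, separate lack of a freezer from declining home storage. State the suspension date used, since 10.6.5 gives none.

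The cost is small. No new procedure is needed: sampling dates are already written on every sample (Sample labelling and transport). The team must record which of the two 10.6.5 reasons applied. Section 8.4 asks only for a reasonable effort to learn why a woman stopped, but here the study team applies the rule itself. The interval for (a) will be wider: if it held 100 women (assumed) at 80%, the half-width would be 1.96 × √(0.80 × 0.20 / 100) = 7.8 points, against 5.5 for 200.

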9.3 Study Visit Phase

There will be four study visits (Visit 1, Visit 2, Visit 3, and Visit 4) for each participant:

- Visit 1: as soon as possible following screening, aiming up to 16 weeks and 6 days gestational age (early in pregnancy)
- Visit 2: 20 gestational weeks or any time in 2nd trimester from 17 weeks and 0 days gestational age to 26 weeks and 6 days gestational age (mid pregnancy)

- Visit 3: 28 gestational weeks or any time in 3rd trimester from 27 weeks and 0 days gestational age onwards (late in pregnancy)
- Visit 4: from the time of birth to 1 week postnatal age (postpartum period)

The timing for each visit was chosen following a discussion with the obstetric member of the trial management team ([name]) and our PPI group (the South London Maternal and Paediatric Infection & Immunity Patient and Public Involvement group) to strike a balance of coinciding with routine antenatal appointments for the convenience of the participants to promote on-going participation, and capturing samples throughout pregnancy at varying gestational stages. Where a visit is not possible to coincide with routine antenatal (or postnatal) appointments (in particular Visit 1), this will then take place in a clinical setting, and if still not possible, in the participant's home.

9.3.1 Visit 1

At Visit 1, after the participant has signed the written informed consent, the relevant study procedures can be performed in any order, which are:

- Background questionnaire
- Contact questionnaire
- Self-sampling of saliva, urine and vaginal secretions
- Venous blood sampling where consent is obtained

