The participant will be reminded to let the study team know when they are in labour/have delivered. A reminder text will also be sent to all participants at 37 gestational weeks to remind them to let the study team know when they are in labour/have delivered. Effort will be made to perform Visit 4 when the participant is still on the postnatal ward provided this also suits the participant. If this timing is not suitable, Visit 4 can be performed at a different time within the first postnatal week, either at home or at a clinical setting, provided the participant is happy to bring her newborn with her to perform the newborn saliva sample. A face-to-face contact with the participant will be necessary to collect the saliva sample from the newborn for cCMV screening.

In the event that the participant delivers prematurely, provided the participant is still happy to remain in the study and the investigator has no concern with the participant remaining in the study, the specified visit number for this will be the subsequent visit of the previous visit and no further visits will be required (for example if the participant delivers her newborn at 32 weeks and the last visit she had was Visit 2, this will be Visit 3 labelled study visit equivalent to Visit 4).

Study Procedures	Screening	Visit 1	Visit 2	Visit 3	Visit 4
Eligibility criteria	X				
Informed consent		X			
Background questionnaire		X			
Contact questionnaire		X	X	X	X
Self-sampling of saliva, urine & vaginal secretions		X	X	X	X
Venous blood sampling*		X	X	X	X
Feedback questionnaire					X
Salivary swab of newborn*					X

At Visit 4, the relevant study procedures are:

- Self-sampling of saliva, urine and vaginal secretions
- Venous blood sampling where consent is obtained
- Screening newborn for cCMV
- Contact questionnaire
- Feedback questionnaire

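### The single all-or-nothing completion percentage in section 13.4.3 mixes drop-out with partial compliance, and no other planned percentage separates the two

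*Combined protocol and SAP*

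**What the plan says.** Section 14.2.2 lists as a secondary endpoint "Proportion of subjects completing the study". Section 13.4.3 makes it operational as "the percentage of participants who complete the study (provide urine, saliva and vaginal secretion samples and questionnaire data at all four study visits"; blood and newborn saliva samples are not needed to count. Section 9.3 sets the schedule: "There will be four study visits (Visit 1, Visit 2, Visit 3, and Visit 4) for each participant".

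Two other provisions decide who can meet that definition.

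- **Section 8.4** covers a woman who, after Visit 1, wants to withdraw because of part of the procedures; the examples given are "non-compliance to vaginal secretion sampling or venous blood taking". She is asked to stay and "complete the rest of the study procedures that the participant is willing to comply with".
- **Section 9.3.4** covers premature delivery. The delivery visit takes the next visit number and "no further visits will be required". The section's own example is a woman who delivers at 32 weeks after Visit 2; her delivery visit is labelled Visit 3 and treated as equivalent to Visit 4.

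**The concern.** Section 8.4 sets out to keep women who decline one procedure, and they remain useful. The primary endpoint in section 14.2.1 needs detection in any one fluid, so a woman who stops vaginal swabs still contributes through saliva and urine. In the completion percentage, however, she scores the same as a woman never seen after Visit 1. So does a woman who gave every sample but left one emailed questionnaire unanswered.

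The study's stated aim is the feasibility of larger studies. Planning one needs two quantities: how many women can be followed to delivery (attrition), and which samples they stop giving (yield). They call for different responses, since attrition drives the number enrolled while yield drives the choice of fluids and sampling method. A low completion percentage on its own does not show which problem the study met.

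**Working it through.** **Is there a figure to reproduce?** The documents state none for completion, retention, drop-out or missing items. Section 13.3.1 addresses precision for the primary endpoint only. What follows therefore checks the definition and then shows a range under stated assumptions.

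**Step 1. How each type of woman is classified**

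| Woman | Followed to delivery? | Completer under 13.4.3? |
|---|---|---|
| Leaves after Visit 1 | No | No |
| Stops vaginal swabs, continues the rest (8.4) | Yes | No |
| Declines blood only (8.4) | Yes | Yes, if all else is given |
| All samples given, one questionnaire missed | Yes | No |
| Delivers prematurely after Visit 2, gives everything asked (9.3.4) | Yes | No; only three visits take place |
| Misses a visit during COVID-19 suspension, later resumes (10.6.5) | Yes | No |

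One label covers the woman who left and four kinds of woman who did not.

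**Step 2. Does another planned summary separate them?**

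- Section 13.4.1 has patient flow in its heading, but its text covers baseline data, the consent percentage and a comparison of consenters with non-consenters.
- The visit-by-fluid percentages in 13.4.3 are of women with CMV detected, not of women who gave a sample.
- The graphical summary in 13.4.3 covers sample type and visit number, but promises no percentage of enrolled women and no split by reason.
- Section 13.4.5 restricts an analysis to women with samples at all three time points, without saying why others lack them.

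No planned percentage of enrolled women does it.

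**Step 3. Possible size of the gap**

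Let R be the share of women followed to delivery. R = 90% is an assumption, as are f and q below.

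(a) Misses concentrated in a fraction f of retained women: completion = R × (1 − f), gap = R × f.

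| f | Completion | Gap (points) |
|---|---|---|
| 2% | 0.90 × 0.98 = 88.2% | 1.8 |
| 5% | 0.90 × 0.95 = 85.5% | 4.5 |
| 10% | 0.90 × 0.90 = 81.0% | 9.0 |
| 20% | 0.90 × 0.80 = 72.0% | 18.0 |

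(b) Each item missed independently with probability q. Items: (3 fluids + 1 questionnaire) × 4 visits = 16. Completion = R × (1 − q)^16.

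| q | Completion | Gap (points) |
|---|---|---|
| 0.5% | 0.90 × 0.923 = 83.1% | 6.9 |
| 1% | 0.90 × 0.851 = 76.6% | 13.4 |
| 2% | 0.90 × 0.724 = 65.1% | 24.9 |
| 5% | 0.90 × 0.440 = 39.6% | 50.4 |

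If the four Visit 1 items are taken as already given, 12 remain. At q = 5%, completion is 0.90 × 0.95^12 = 0.90 × 0.540 = 48.6%, a gap of 41.4 points.

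**Step 4. What an observed figure can tell the next study**

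A completion of 72% fits R = 72% with no missed items (0.72 × 1.00), R = 80% with f = 10% (0.80 × 0.90), and R = 90% with f = 20% (0.90 × 0.80). Inflating a future sample for drop-out would need a factor of 1/0.72 = 1.39 in the first case and 1/0.90 = 1.11 in the last. The completion percentage cannot tell these apart.

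**The case against.** The strongest reply is that section 13.4.3 says openly what it counts. It defines full completion and never calls it retention, and a strict declared outcome is not a biased estimate of something else. That is right, and it limits the point: what is missing is an estimate, and the existing one is not wrong.

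Two stronger readings are tempting, and the documents support neither.

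- **That the percentage will badly understate retention.** With no drop-out or missing-item rate in the documents, the gap could be trivial. The large values rest on independent misses. The three fluids are self-sampled on the day of the visit, so misses probably cluster within women and visits, which shrinks the gap.
- **That sections 8.4 and 13.4.3 contradict each other.** One governs conduct and the other defines an outcome; both can stand. Blood, one of the two examples in 8.4, is exempt from the completion rule in any case.

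Other material bears on why women stop. Section 8.4 asks for a reasonable effort to learn the reason for leaving and offers the feedback questionnaire at withdrawal. Section 13.4.3 analyses acceptability, and section 9.5 (Process Evaluation) plans interviews with up to 20 mothers. Per-visit detection percentages would also normally be shown with denominators. These sources can suggest which procedure is unpopular, but none commits the study to a retention or provision percentage.

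Finally, no progression threshold is attached to completion, and the extra rows could be tabulated at reporting. That lowers the urgency. It does not remove the case for defining them now, since the definitions need choices, notably for premature delivery, that are better made before the data are seen.

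**Conclusion.** The point holds as a gap in what will be estimated. The all-items, all-visits rule combines withdrawal, refusal of one fluid, a missed questionnaire and a schedule shortened by premature delivery, and nothing else planned separates them. Completion cannot exceed the share followed to delivery and may fall below it. At an assumed 90% retention the shortfall is about 2 points if 2% of retained women miss any item, and about 50 points if each of 16 items is missed independently 5% of the time. The documents do not say where in that range the study will fall.

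Women who deliver prematurely before Visit 3 are a separate defect: for them the definition is unattainable however fully they comply. The consequence is confined to the feasibility conclusions; the primary endpoint estimate is untouched.

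**What to change.** Keep the existing percentage in section 13.4.3, label it full completion, and add the following, each with a 95% confidence interval (none is stated for completion at present):

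1. **Retention:** the percentage of enrolled women who provide at least one sample or questionnaire at Visit 4, or at the delivery visit that section 9.3.4 treats as equivalent to Visit 4. Tying it to the label Visit 4 alone would wrongly count some women with premature delivery as lost.
2. **Provision:** for each fluid and for the questionnaire, the percentage of enrolled women providing it at each visit, with women continuing in part under section 8.4 shown separately from full withdrawals.

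Also state that a woman with premature delivery who provided every item at all the visits required of her counts as a completer.

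Use the first estimate for attrition and the second for sample yield when planning the larger study. With 200 women, the usual half-width 1.96 × √(p(1 − p)/200) is 4.2 points at p = 90% and 6.9 points at p = 50%, so both would be informative. The cost is a short change of wording and a few more descriptive percentages; the study already collects the data.
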